##### 2.10.2.2 Evaluation of Early Response of DS AML to Treatment by MRD

Data collected from 146 patients in the recently completed study AAML0431 provide direct evidence for the prognostic value of MRD measured by flow cytometry after Induction I in DS AML. The unique immunophenotype of DS AML blasts permitted their detection by multi-parameter flow cytometry at a level as low as 0.01% ([name], personal communication). EFS among 125 patients who were MRD-negative (MRD  $< 0.05\%$ ) was significantly higher than in 21 patients (14%) who were MRD-positive (93% v. 76% at 2 years; log-rank  $P = .007$ ). This difference extended to OS (2-yr OS 96% v. 76%, log-rank  $P < 0.001$ ), indicating that the prognostically unfavorable group of DS AML patients can be identified by MRD and that this cohort may benefit from intensification of therapy. Complying with the FDA requirement that the MRD cut-off be above the threshold of sensitivity of the assay, AAML1531 will use a cutoff of 0.05%. Based on the data of AAML0431, this cut-off safely captures the large majority of MRD-negative patients for the proposed reduction in therapy (only 5 patients had MRD levels between 0.01 and 0.1%, with 2 of these patients relapsing, 1 electively

withdrawing at the end of induction, and 2 patients remaining in remission).

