### 9.2 Patient Accrual and Expected Duration of Trial

AAML1531 will be compared against a fixed 2-year EFS of 93.5% for SR patients and 76% for HR patients which were observed for comparable patients treated on the prior COG study of DS AML patients (AAML0431). For SR patients, assuming a null EFS of 93.5% at 2 years, there is 95% power to detect an alternative EFS of 87% at 2 years with 1-sided testing at the 10% level of statistical significance if there are 200 SR patients who continue to Induction II. For HR patients, assuming a null EFS of 76% at 2 years, there is 80% power to detect an alternative EFS of 88% at 2 years with 1-sided testing at the 10% level of statistical significance if there are 41 high risk patients who continue to Induction II. The necessary sample size was computed using a binomial test. The final analysis of EFS will occur after a minimum of 2 years after the last patient is enrolled.

\* Replaced with Amendment #6

Up to 3% of patients enrolled are expected to be found ineligible, up to 3% are expected to go off protocol therapy at the end of Induction I, and approximately 83% of patients are expected to be SR. Therefore, enrollment of up to 256 patients will be required to assure that there are 200 SR patients who continue to Induction II and there are 41 HR patients continue to Induction II. Based on an accrual estimate of 60 patients per year, accrual of 256 patients is expected to be completed in approximately 4.3 years.

\* Updated with Amendment #4A

As of October 22, 2018, 26 of the 143 patients enrolled are HR patients who continued to Induction II. Up to 3% of patients enrolled are expected to be found ineligible, up to 3% are expected to go off protocol therapy at the end of Induction I, and approximately 83% of patients are expected to be SR. Therefore, enrollment of up to 256 patients will be required to assure that there are 41 HR patients who continue to Induction II. Based on an accrual estimate of 60 patients per year, accrual of an additional 113 patients is expected to be completed in approximately 2 years.

\* Updated with Amendment #6

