### 15.1 Exploratory Aims

15.1.1 To determine the extent to which elimination of HD Ara-C from treatment of standard risk DS AML decreases adverse events and resource utilization in children with DS. With amendment #4A, this exploratory aim is complete.

Comparison will be made to predecessor study AAML0431, which included treatment with HD Ara-C. Since the first cycle of induction therapy is identical in both studies, comparison will be made for the time interval from end of Induction I to the completion of protocol therapy. Specifically, we will determine if elimination of HD Ara-C from treatment of standard risk DS AML results in:

15.1.1.1 A significant decrease of the number of days per patient spent on protocol therapy compared to predecessor study AAML0431.

Subjects who are MRD negative following Induction I, will continue on Arm A for SR patients with the elimination of HD Ara-C. We hypothesize that the elimination of the cycle of HD Ara-C will result in overall shorter treatment duration by reducing the total number of cycles of therapy as well as less cumulative myelotoxicity that might contribute to delays in starting subsequent cycles. A two-sample t-test will be used to compare average number of days per patient spent on protocol therapy for standard risk patients on AAML1531 compared to patients treated on AAML0431.

15.1.1.2 A significant decrease of the average number of days of hospitalization per patient compared to predecessor studies AAML0431 and A2971.

We similarly anticipate that the duration of hospitalization throughout protocol therapy will be reduced. The number of days in hospital will be determined for patients treated on AAML1531 Arm A and compared with the predecessor study A2971. A2971 patients with DS AML less than 4 years of age stayed a mean of 35.1 days in hospital (standard deviation 18.9) after the start of Induction II through the remainder of protocol therapy. Data regarding days of hospitalization during protocol treatment were not collected for study AAML0431. These data, however, are available for a subset of patients who were

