treated at centers contributing data to the Pediatric Health Information Systems (PHIS) database. Data from AAML0431 will be merged with PHIS resource utilization data as previously described. Based on this prior experience, approximately 40% of patients enrolled on AAML0431 will have PHIS data available. Two-sample t-test will be used to compare average number of days of hospitalization per patient for standard risk patients on AAML1531 compared to patients treated on AAML0431 and A2971.

15.1.1.3 A significant decrease of the number (per patient) and rate (per duration of treatment) of sterile site infections compared to the predecessor study AAML0431.

In addition, we hypothesize that the elimination of HD Ara-C will lead to less morbidity compared to patients whose treatment historically included this cycle. On the predecessor study, AAML0431, the greatest number of adverse events occurred during the administration of HD Ara-C (27.5% of the total reported), with 65% of adverse events classified as Grade 3 or greater (6.5% were Grade 4). These included Grade 3 or greater sterile site bacterial infection in 23% of patients and febrile neutropenia in 30% of patients, resulting in the need for continuous hospitalization. We anticipate fewer sterile site infections for patients with DS AML being treated on AAML1531 without HD Ara-C compared with the predecessor study, AAML0431, which included the use of HD Ara-C. The number (per patient) and rate (per duration of treatment) of sterile site infections of patients treated for DS AML on Arm A will be compared to AAML0431 after the start of Induction II. Poisson regression will be used to compare rate (per duration of treatment) of sterile site infections for standard risk AAML1531 patients with AAML0431 patients.

15.1.1.4 A significant decrease of resource utilization by AML treatment compared to the predecessor study AAML0431.

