Given our anticipation of fewer sterile site infections and shorter hospitalization, we hypothesize that the elimination of HD Ara-C on AAML1531 will ultimately result in decreased resource utilization (after the start of Induction II on AAML1531 Arm A), as sepsis is the single most important factor determining length of stay and hospital costs in the treatment of children with leukemia. Resource utilization will be compared between patients on AAML0431 and AAML1531 at PHIS sites by comparing rates of inpatient resource utilization including antimicrobial usage, ICU level care resources, standard pharmaceutical supportive care measures, and blood products. PHIS adjusted inpatient costs will also be compared between patients enrolled on AAML0431 and AAML1531. These measurements of resource utilization and standardized costs will be compared between the current treatment protocol (Arm A, no HD Ara-C cycle) and predecessor study AAML0431, which included the use of HD Ara-C.

These data on duration of therapy, length of hospital admission and sterile site infections are routinely submitted for patients with AML. Analysis of these exploratory objectives is expected to measure potential gains made for SR DS AML patients by decreasing the numbers of adverse events through a reduction in treatment intensity.

**15.1.2 To compare feasibility and analytical characteristics of flow cytometry, PCR and targeted error-corrected sequencing of *GATA1* mutations as methods to detect MRD in DS AML (Exploratory aim 1.2.1)**

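### The toxicity and resource aims compare MRD-negative AAML1531 children with AAML0431 patients not restricted by MRD, so a case-mix bias of unknown sign and size is possible

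*Combined protocol and SAP*

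**What the plan says.** Section 15.1.1 sets out to measure how far removing HD Ara-C from standard-risk treatment reduces adverse events and resource use between the end of Induction I and the end of protocol therapy. Section 3.3.5 defines standard risk as marrow MRD below 0.05% at the end of Induction I. The comparison groups are named as follows.

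- **15.1.1.1, days on therapy:** a two-sample t-test to "compare average number of days per patient spent on protocol therapy for standard risk patients on AAML1531 compared to patients treated on AAML0431".
- **15.1.1.2, hospital days:** a two-sample t-test of average days of "hospitalization per patient for standard risk patients on AAML1531 compared to patients treated on AAML0431 and A2971". For AAML0431 these data exist only through the PHIS database, for about 40% of patients.
- **15.1.1.3, sterile site infections:** "Poisson regression will be used to compare rate (per duration of treatment) of sterile site infections for standard risk AAML1531 patients with AAML0431 patients". The aim also names the number of infections per patient.
- **15.1.1.4, resource use:** "Resource utilization will be compared between patients on AAML0431 and AAML1531 at PHIS sites".

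None of the four restricts AAML0431 by MRD, and no stratum or covariate is named. Efficacy is handled differently. Section 9.2 uses separate standard-risk and high-risk EFS values (93.5% and 76%), "observed for comparable patients treated on the prior COG study of DS AML patients". Section 9.3.2 models the AAML0431 standard-risk curve separately, for patients who continued to Induction II.

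Section 2.10.2.2 describes the AAML0431 MRD evidence: "Data collected from 146 patients in the recently completed study AAML0431" were used, and EFS in the 125 MRD-negative patients was significantly "higher than in 21 patients (14%) who were MRD-positive". Section 15.1.1 also states that this exploratory aim is complete with Amendment 4A.

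**The concern.** The question is about standard-risk children, but only one side of each comparison consists of them. The AAML0431 side also contains MRD-positive children and children with no MRD result. An unadjusted difference then mixes two things: the effect of removing HD Ara-C, and any difference in outcome between MRD-negative children and that mixed group.

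The MRD-positive group is known to differ in prognosis: 2-year EFS was 76% against 93% (Section 2.10.2.2). It could also differ in infections, hospital stay or early end of therapy. Arm A was closed for inferior EFS (Section 2.9), so the toxicity and resource results are the other side of that trade-off. They should describe the same kind of child as the EFS result.

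**Working it through.** **1. The plan's own figure.** 21/146 = 14.4%, which reproduces the stated 14%. It applies only to patients with MRD data. AAML0431 had 205 patients (Section 2.5), so 205 − 146 = 59 (28.8%) have none. The MRD-positive share of all 205 lies between 21/205 = 10.2% and (21 + 59)/205 = 39.0%. Using 14.4% for the whole comparator assumes that the untested resemble the tested.

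**2. Expected change in infections from dropping the HD Ara-C cycle.** Inputs are the AAML0431 cycles after Induction I in Table 2 (Section 2.4). The table gives the percentage of patients infected per cycle, used here as a rough proxy for counts, and median cycle lengths.

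| | Infections per 100 patients | Days (sum of medians) | Per 100 patient-days |
|---|---|---|---|
| All five cycles | 22.6 + 11.3 + 8.8 + 12.7 + 8.4 = 63.8 | 42 + 32 + 34 + 35 + 35 = 178 | 0.358 |
| Without HD Ara-C | 63.8 − 22.6 = 41.2 | 178 − 42 = 136 | 0.303 |

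The rate per day changes by 0.303/0.358 − 1, about −15%. The number per patient changes by 41.2/63.8 − 1, about −35%.

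**3. Case mix, infections.** Let r be the ratio of the infection rate in MRD-positive to that in MRD-negative children. The documents do not give r, so the values are assumptions. With no true treatment effect and a share w = 0.144, the apparent ratio is 1/(1 + w(r − 1)).

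| Assumed r | Apparent ratio | Spurious change |
|---|---|---|
| 0.75 | 1.04 | +4% |
| 1.5 | 0.93 | −7% |
| 2 | 0.87 | −13% |

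At r = 1.5 to 2, this is about half to most of the −15% per-day change, but only about a fifth to a third of the −35% per-patient change. At the share limits in step 1, r = 2 gives 1/1.102 = 0.91 and 1/1.390 = 0.72.

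**4. Case mix, days on therapy.** The shift is 0.144 × d, where d is the MRD-positive mean minus the MRD-negative mean (also not given). It is 1.4 days at d = 10, 4.3 at d = 30 and −4.3 at d = −30. Against the roughly 42 days removed by design, these are 3%, 10% and −10%. To reach 25% of 42 days, d would have to be 10.5/0.144 = 73 days.

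**5. Case mix, hospital days.** Inputs are SD 18.9 (A2971, Section 15.1.1.2), 109 standard-risk patients (Section 2.9), and 0.40 × 205 = 82 AAML0431 patients with PHIS data. The standard error is 18.9 × √(1/109 + 1/82) = 2.76. With no true effect and an assumed two-sided 5% test, the chance of a false significant decrease is Φ(0.144d/2.76 − 1.96). It is 2.5% at d = 0, 4.5% at d = 5, 7.5% at d = 10 and 16.5% at d = 18.9.

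**The case against.** The strongest reply is that little depends on this. The aim is exploratory, is marked complete with Amendment 4A and no longer appears in Section 1.2. Section 15.0 says these results do not guide treatment, and Arm A is closed. That stands and lowers the weight of the point. It does not cure the mismatch: the specification remains in the current protocol, and the documents report no result from it.

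A reader might infer more: that part of any observed decrease is bound to be case mix, with the removal of HD Ara-C credited for leaving out poor responders. The documents do not support this.

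- **Direction.** Nothing gives infections, hospital days or treatment duration by MRD status. The bias could run the other way. Section 2.10.2.2 reports 7 MRD-positive patients among the 12 relapses with MRD data. If these come from the groups above, relapse occurred in 7/21 (33%) against 5/125 (4%). Relapses that ended therapy early would shorten the AAML0431 average and hide a decrease; their timing is not given.
- **Non-responders.** MRD-positive children are not simply non-responders. Section 4.1.5 allows for morphologic remission with positive MRD.
- **Share.** The 14.4% cannot be read as the share of all 205.

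The remedy also has limits. AAML1531 uses a different flow-cytometry method from AAML0431 (Section 2.10.2.2), so the same 0.05% cut-off does not give exact matching. Restricting to known MRD-negative patients also drops the 59 untested, which could introduce a selection of its own. Both call for a caveat and a sensitivity analysis. Finally, measuring from the end of Induction I already largely implies continuation to Induction II; what is missing is the MRD restriction.

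**Conclusion.** The concern holds in this form: the AAML0431 comparator in 15.1.1.1 to 15.1.1.4 does not match the standard-risk question, while the EFS benchmark does. A case-mix bias of unknown sign and size is possible. For infections, assumed rate ratios of 0.75 to 2 give spurious changes from +4% to −13%, which could matter beside an expected −15% per day and matters less beside −35% per patient. For days on therapy the shift is probably small beside about 42 days. For hospital days it could raise the false-positive chance noticeably, but only if MRD-positive children stay several days longer. All of these rest on assumed differences by MRD status and on the 14.4% share holding among the untested. Severity is minor: this is a cheap improvement to an exploratory aim already marked complete.

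**What to change.** For the analysis or report of aims 15.1.1.1 to 15.1.1.4:

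1. Make the main AAML0431 comparator the patients with MRD below 0.05% at the end of Induction I who continued to Induction II (at most 125; about 0.40 × 125 = 50 for the PHIS-based outcomes, if 40% applies to them too).
2. Show all AAML0431 patients as a sensitivity analysis, and state how many have no MRD result.
3. Note that the MRD flow method differs between the trials.
4. Label the A2971 hospital-day comparison as not MRD-matched; Section 2.8 describes AAML0431 as collecting the first MRD data in this disease.

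The change needs no new data. If the analyses have already been run, it means rerunning them on the subset, or at least adding the caveat to the report.

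The cost is precision. The hospital-day difference detectable with 80% power is (1.96 + 0.842) × 18.9 × √(1/109 + 1/n), assuming a two-sided 5% test. In the PHIS subset it rises from 7.7 days (n = 82) to 9.0 days (n = 50). If every AAML0431 patient had hospital data, it would rise from 6.3 days (n = 205) to 6.9 days (n = 125).

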## 2.5 Safety and Feasibility of Lower Intensity Treatment Protocols for Standard Risk DS AML

A series of observations supports the feasibility of reducing treatment intensity for the majority of patients with DS AML. Chemotherapy of standard intensity resulted in superior survival for children with DS compared to the general pediatric population. In contrast to patients with non-DS AML, DS AML patients enrolled in study CCG 2891 had superior outcomes with standard timing of induction elements (DCTER-DCTER) compared with intensive timing. Study A2971, the first DS-specific AML trial conducted by COG and legacy groups, used CCG 2891-based therapy (with standard timing of DCTER-DCTER induction) but eliminated dexamethasone and etoposide. Despite this reduction, outcomes remained comparable (A2971: OS 84 $\pm$ 6%, EFS 79 $\pm$ 7%, disease-free survival, DFS 89 $\pm$ 6%; CCG 2891: OS 79 $\pm$ 7%, EFS 77 $\pm$ 7%, DFS 85 $\pm$ 6%). Finally, Japanese investigators using pirarubicin (25 mg/m^2/d for 2 days), cytarabine (100 mg/m^2/d for 7 days), and etoposide (150 mg/m^2/d for 3 days) achieved an excellent survival outcome (4 year EFS 83.3%) using a treatment protocol for DS AML that did not contain cycles of HD Ara-C. Based on these observations, HD Ara-C will be eliminated in study AAML1531 from the treatment of patients with standard risk DS AML (approximately 85%).

The administration of daunorubicin as a continuous infusion (over 96 hours) was successfully used in both predecessor studies of DS AML, A2971 (n = 132) and COG AAML0431 (n = 205). There have been no reports of excessive mucosal toxicity, adverse events related to drug administration or significant acute cardiac toxicity. At the same time,

continuous infusion of anthracyclines could not be shown to provide a benefit of lower cardiotoxicity compared to bolus infusion. Therefore, in study AAML1531 daunorubicin will be administered as short minute infusion, rather than the previously used continuous infusion over 96 hours. The cumulative dose of anthracycline in the standard risk group (240 mg/m^2) remains identical to that of AAML0431, while patients in the high risk group will receive 272 mg/m^2. The use of dexamethasone will be allowed in the current study as per institutional preference (refer to [Section 4.1.7](#) for additional information).

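### Hospital days: the AAML0431 comparator is only the roughly 40% of patients at PHIS centers, while no PHIS restriction is stated for AAML1531 (Section 15.1.1.2)

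*Combined protocol and SAP*

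**What the plan says.** The hospital-days comparison is in Section 15.1.1.2.

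- **AAML0431 side.** "Data regarding days of hospitalization during protocol treatment were not collected for study AAML0431". The plan then explains that the days can be had for patients at centers contributing to PHIS: "Data from AAML0431 will be merged with PHIS resource utilization data as previously described". On coverage: "approximately 40% of patients enrolled on AAML0431 will have PHIS data available".
- **AAML1531 side.** "The number of days in hospital will be determined for patients treated on AAML1531 Arm A". No restriction by site is attached. The closing paragraph of Section 15.1.1 describes length of admission as an item routinely submitted for AML patients, without naming the form, the source or the set of sites.
- **Test.** A two-sample t-test will "compare average number of days of hospitalization per patient for standard risk patients on AAML1531 compared to patients treated on AAML0431 and A2971". No adjustment for site, common data source, significance level or sidedness is given.
- **Sibling aim.** For resource use, Section 15.1.1.4 says: "Resource utilization will be compared between patients on AAML0431 and AAML1531 at PHIS sites". The match on site type is explicit there and absent from 15.1.1.2.
- **Status.** Section 15.1.1 declares the aim complete with amendment #4A, and Section 1.2 no longer lists it.

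**The concern.** The comparison is meant to show that omitting HD Ara-C shortens hospital stay. Read literally, it sets AAML1531 standard-risk children from any participating center against AAML0431 children from PHIS centers only. Length of stay depends on local discharge practice as well as on treatment. Section 3.1.2 provides for international sites, so AAML1531 may include hospitals of a kind that the AAML0431 subset lacks. A difference between PHIS and other hospitals would then be read as a treatment effect.

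There may be a second mismatch. AAML0431 days come from an administrative database. If AAML1531 days come from trial data submission, the two trials count days differently, and this applies to every patient rather than only to those outside PHIS.

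The result would be the plan's estimate of hospital days saved on a regimen that Section 2.9 reports as having lower EFS. No EFS analysis or treatment decision depends on it.

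**Working it through.** The plan gives no sample size, power or detectable difference for this comparison, so there is no figure of its own to reproduce. What follows is a sensitivity calculation.

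**Inputs from the documents**
- AAML0431 total: 205 (Section 2.5). PHIS subset: 0.40 × 205 = 82.
- AAML1531 standard-risk patients: 109 as of 5 October 2018 (Section 2.9).
- SD of hospital days: 18.9, mean 35.1, from A2971 (Section 15.1.1.2), used as a proxy for both groups.

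**Assumptions not in the documents**
- PHIS share on AAML1531, p = 40% (range 20% to 60%).
- Difference in mean stay between non-PHIS and PHIS hospitals, d = 2 to 10 days.
- Shift between data sources, s = 2 to 5 days.
- Two-sided 5% test and no true treatment effect.

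**Step 1: bias.** All AAML0431 patients in the contrast are at PHIS centers, and a share 1 − p of AAML1531 patients are not. The site-mix bias is therefore (1 − p)d, or 0.6d at p = 40%. For d = 5 it is 4, 3 or 2 days at p = 20%, 40% or 60%. A data-source shift enters in full, as s.

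**Step 2: standard error as written.** 18.9 × √(1/109 + 1/82) = 2.76 days.

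**Step 3: chance of rejecting with no treatment effect,** P(|Z + bias/2.76| > 1.96):

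| Assumed mismatch | Bias (days) | Rejection probability |
|---|---|---|
| Site difference d = 2 | 1.2 | 7% |
| Site difference d = 5 | 3.0 | 19% |
| Site difference d = 10 | 6.0 | 58% |
| Data-source shift s = 2 | 2.0 | 11% |
| Data-source shift s = 5 | 5.0 | 44% |

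The aim is directional, so the sign matters. At d = 5, bias/SE = 3.0/2.76 = 1.09. If non-PHIS stays are the shorter ones, the chance of falsely declaring a decrease is about 19%. If they are the longer ones, it is P(Z < −1.96 − 1.09), about 0.1%, and a real decrease would be masked instead.

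**Step 4: precision after matching.** At p = 40%, 0.40 × 109 ≈ 44 AAML1531 patients remain, and the SE is 18.9 × √(1/44 + 1/82) = 3.53 days. The difference detectable with 80% power, (1.96 + 0.84) × SE, rises from 7.7 to 9.9 days. At p = 20% (22 patients) the SE is 18.9 × √(1/22 + 1/82) = 4.54. At p = 60% (65 patients) it is 18.9 × √(1/65 + 1/82) = 3.14.

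**The case against.** **The aim is exploratory and closed.** It is declared complete, Arm A is shut, and Section 15.0 says these results do not guide treatment. This stands and sets the severity. It does not make the stated comparison sound, and the method text is still in the current plan.

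**The site and source claims are inferred.** A reader might conclude that AAML1531 days come from all sites on study forms. The documents do not say so. They state no restriction, and they describe admission data as routinely submitted. The missing restriction is a matter of text. The data-source mismatch is conditional.

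**The rejection rates are hypothetical.** A reader might take 19% or 58% as the test's false-positive rate. The documents support no such figure: d, its sign, the PHIS share and the two-sided level are all assumed. Nor are 205 and 109 analysis counts. The first is the whole of AAML0431, although the comparison starts after Induction I. The second was taken days before Arm A closed. The rates show sensitivity only.

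**There is a second comparator.** The A2971 comparison uses that trial's own mean and SD and is not described as PHIS-limited. A reader might infer that the whole hospital-days analysis fails, but the problem lies in the AAML0431 half alone. The plan also discloses the 40% coverage openly.

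**PHIS matching does not cure everything.** This is correct. Section 9.3.1 says Arm A patients were to be taken off protocol therapy at closure, which could shorten their recorded stay. The AAML0431 comparator is also not limited to MRD-negative patients.

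**Conclusion.** The point holds for the AAML0431 contrast. Followed as written, an unadjusted t-test compares AAML1531 standard-risk patients, with no PHIS restriction, against a PHIS-only subset of AAML0431. Treatment is therefore partly confounded with hospital type. The confounding is partial to the extent that AAML1531 also enrolled at PHIS sites, as 15.1.1.4 presupposes. If AAML1531 days were taken from trial submission, treatment is also confounded with data source.

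The size and direction are unknown. A bias favoring the reduced regimen should not be inferred, since the documents would equally allow the opposite. Under the stated assumptions the site-mix bias is 0.6d, or 3 days for an assumed d of 5, against a mean stay of 35.1 days in A2971.

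Severity is minor: the aim is exploratory and complete, and neither EFS nor any treatment decision depends on it.

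**What to change.** Add a sentence to Section 15.1.1.2 making the main AAML0431 contrast one between AAML1531 standard-risk patients at PHIS sites and AAML0431 patients with PHIS data, with days taken from PHIS in both trials. This carries over the site match already used in 15.1.1.4. Keep the unrestricted AAML1531 result as a labelled secondary analysis, and leave the A2971 comparison as it is. If the aim has already been analysed, rerun it this way or report the mismatch as a limitation.

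In the same place, state how Arm A patients taken off therapy at closure are handled, and whether the AAML0431 group is limited to MRD-negative patients. If it is, and the MRD-negative fraction in Section 2.10.2.2 (125 of 146) applies, about 82 × 125/146 = 70 remain. The SE with 44 AAML1531 patients is then 18.9 × √(1/44 + 1/70) = 3.64 days.

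The drafting cost is small. The merge is explicit for AAML0431 and implied for AAML1531 by 15.1.1.4, so access to the AAML1531 linkage should be confirmed. The statistical cost is a wider interval: SE about 3.5 instead of 2.8 days, assuming a 40% PHIS share, SD 18.9, and 109 and 82 patients before restriction. Any rejection rates should be reported only as sensitivity figures under a named site difference.

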**Table 2: Adverse events per cycle in predecessor study AAML0431**

Cycle	Median number of days on cycle (range)	Time to ANC recovery (median, days)	ICU admission (% of patients)	Febrile neutropenia Grade $\geq 3$ (% patients)	Sterile site bacterial infection Grade $> 3$ (% patients)
Induction I TAD	34 (15-66)	30	7	27	19.2
Induction II HD Ara-C	42 (27-69)	37	7	29.7	22.6
Induction III TAD	32 (20-59)	28	2	6.2	11.3
Induction IV TAD	34 (22-63)	28	2	5.6	8.8
Intensification I Ara-C/Etoposide	35 (27-58)	33	4	11.5	12.7
Intensification II Ara-C/Etoposide	35 (22-124)	32	1	12.4	8.4

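### Sterile site infection rates are compared by Poisson regression with no stated allowance for extra-Poisson variation, so standard errors may be too small

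*Combined protocol and SAP*

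**What the plan says.** Section 15.1.1.3 asks whether dropping HD Ara-C from standard risk treatment gives "A significant decrease of the number (per patient) and rate (per duration of treatment) of sterile site infections" relative to AAML0431. Arm A "will be compared to AAML0431 after the start of Induction II", which means four cycles on Arm A against five on AAML0431. For the rate, the whole specification is one sentence: "Poisson regression will be used to compare rate (per duration of treatment) of sterile site infections for standard risk AAML1531 patients with AAML0431 patients". No test is named for the number per patient. No alpha, sidedness, power or effect size is given for this comparison. Nothing is said about dispersion, robust standard errors, or whether the unit is the child or the child-cycle.

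Three other places bear on the weight of the point. Section 9.1 lists infection rates among the other outcome measures. Section 15.0 says the exploratory studies are for research only and do not guide treatment. Section 15.1.1 declares this aim complete with amendment #4A.

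**The concern.** The outcome is a count per child, with days on treatment as exposure. The Poisson model sets the variance of that count equal to its mean. This fails if children have different underlying infection rates, if one infection makes another more likely, or if children contribute different mixes of cycles that carry different rates.

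All three are plausible here. Section 3.2.4 sets no minimum organ function and allows prior cardiac repair. Section 9.3.1 says standard risk children enrolled before amendment #4A were to be taken off protocol therapy, so not all completed every cycle. Where the variance exceeds the mean, a model-based Poisson standard error is too small, the interval too narrow, and a decrease in infections is declared too easily. The end of Section 15.1.1.4 expects these analyses to measure what standard risk children gained from reduced intensity. Arm A closed for inferior EFS, so the toxicity side of that trade-off should carry an honest interval.

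**Working it through.** The plan states no sample size or power for this comparison, so there is no figure to reproduce. The check asks how far the test level could move.

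**Inputs from the documents**

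Section 2.4, Table 2 ("Adverse events per cycle in predecessor study AAML0431"), cycles after Induction I. The row for the HD Ara-C cycle reads "42 (27-69) 37 7 29.7 22.6": the first figure is median days and the last is the percentage of patients with a sterile site infection. Read the same way, the five rows give:
- Induction II (HD Ara-C): 22.6% of patients, median 42 days
- Induction III (TAD): 11.3% of patients, median 32 days
- Induction IV (TAD): 8.8% of patients, median 34 days
- Intensification I: 12.7% of patients, median 35 days
- Intensification II: 8.4% of patients, median 35 days

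Patients: 109 standard risk on AAML1531 (Section 2.9, as of October 5, 2018) and 125 MRD-negative on AAML0431 (Section 2.10.2.2).

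**Assumed, because the documents do not say:** a 5% alpha; between-child frailty variance θ; median cycle days as exposure; and Table 2 percentages, which cover all AAML0431 patients, applied to standard risk children.

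**Step 1. Mean counts.**
- AAML0431: 0.226 + 0.113 + 0.088 + 0.127 + 0.084 = 0.638 infections per child over 42 + 32 + 34 + 35 + 35 = 178 days.
- Without the HD Ara-C cycle: 0.638 − 0.226 = 0.412 over 178 − 42 = 136 days.
- Rate ratio: (0.412/136)/(0.638/178) = 0.845.

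The means are lower bounds if a child can have more than one infection in a cycle.

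**Step 2. If the variance exceeds the mean.** With gamma frailty, variance/mean is φ = 1 + θ × mean. On AAML0431, θ = 0.5 gives 1 + 0.5 × 0.638 = 1.32, and θ = 1 gives 1.64. The Poisson standard error is then too small by 1 − 1/√φ, which is 13% and 22%. The true two-sided level is 2 × (1 − Φ(1.96/√φ)): 8.0% at φ = 1.25, 11.0% at 1.5 and 16.6% at 2.

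Simulation under equal true rates (20,000 trials per setting, 109 v 125 children) agrees:

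| θ | Poisson SE, two-sided level | Robust SE, two-sided level | Poisson SE, false decrease (2.5% tail) |
|---|---|---|---|
| 0 | 4.9% | 5.2% | 2.3% |
| 0.25 | 6.1% | 4.9% | 2.9% |
| 0.5 | 8.2% | 5.2% | 3.9% |
| 1 | 12.0% | 5.7% | 5.7% |
| 2 | 17.2% | 5.7% | 8.4% |

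With all 205 AAML0431 patients (Section 2.5) as comparator, the Poisson levels at θ = 0.5 and 1 are 7.6% and 11.3%.

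**Step 3. If the variance is below the mean.** Suppose at most one infection is counted per cycle and cycles are independent. Then φ = 1 − Σp²/Σp. On AAML0431, Σp² = 0.0511 + 0.0128 + 0.0077 + 0.0161 + 0.0071 = 0.0948, so φ = 1 − 0.0948/0.638 = 0.85. The Poisson standard error is too large by 1/√0.85 − 1, about 8%, and the true level is 3.4%.

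**Step 4. Unequal cycles alone.** On the Table 2 figures, a child who stopped after one TAD cycle has 0.113/32 = 0.353 infections per 100 days, against 0.412/136 = 0.303 for four cycles, about 17% higher. The squared relative spread is at most about 0.17² = 0.03, far below 0.5. This route adds little by itself; most of any excess would have to come from differences between children.

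**The case against.** The strongest case against the point has four parts.

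**No evidence of excess variance.** A reader might infer that Poisson fails because one child can have several infections, or because Table 2 shows different risks by cycle. Neither follows. The Poisson model allows counts above one, and a sum of independent Poisson counts with different means is still Poisson when every child receives the same cycles. The documents give no per-child counts, and Step 3 shows the error could go the other way. This stands: the standard error may be too small, not will be.

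**Assumed size.** A reader might quote a level of 11% to 17%, from φ of 1.5 to 2. At means of 0.638 and 0.412, φ = 2 needs a frailty variance of 1/0.638 = 1.57 to 1/0.412 = 2.43. Nothing in the documents supports that for children under 4 with one disease on one regimen. This stands too, and it is why the moderate range of 0.5 to 1 is used; even that is an assumption.

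**No change of conclusion.** With 109 × 0.412 = 44.9 and 125 × 0.638 = 79.8 expected infections, the Poisson standard error of the log ratio is √(1/44.9 + 1/79.8) = 0.187. A ratio of 0.845 then has a 95% interval of about 0.59 to 1.22. Multiplying the standard error by √1.5 gives 0.228 and about 0.54 to 1.32. Neither excludes 1. This is fair for the projected figures, but the observed ratio is not in the documents, and the width of the reported interval still changes.

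**Low stakes and silence.** The aim is exploratory and complete, no alpha is set, and a robust variance is an ordinary option within Poisson regression that the text does not rule out. This stands as to severity. It does not show that dispersion was handled.

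**Conclusion.** The point holds as a minor one. Section 15.1.1.3 sets out to show a significant decrease with a model whose variance assumption is neither relaxed nor checked in the text. If between-child frailty variance is 0.5 to 1, a nominal two-sided 5% test has a true level of about 8% to 12%, and the chance of a false decrease in the 2.5% tail rises to about 4% to 6%. Under one-per-cycle counting with independent cycles, the standard error is instead about 8% too large.

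Both results rest on an assumed alpha and on Table 2 percentages standing in for infection counts; the first also rests on the assumed frailty range. The documents do not settle which direction applies, and do not support saying that the reported evidence is overstated. They support saying that the stated method does not protect against it.

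**What to change.** In Section 15.1.1.3, specify Poisson regression with a per-patient robust (sandwich) variance, or negative binomial regression, with log days on treatment as offset, and report the dispersion estimate with the rate ratio and interval. The sandwich variance has the advantage of being valid whether the variance is above or below the mean, so the direction need not be known beforehand; the simulated level stays at 4.9% to 5.7% for θ from 0 to 2. If the analysis has already been run, report this as a sensitivity analysis beside it.

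The cost is one line of model specification on data already collected. The downside is that intervals may be slightly wider: about √1.32 = 1.15 to √1.64 = 1.28 times on the log scale at the AAML0431 dispersion for θ of 0.5 to 1, and little changed if there is no extra variation.
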